3.3. Stopping Criteria

3.3.1. Individual Stopping Criteria^a

In this phase 2a safety study, the following individual stopping rules will apply:

The investigator or sponsor believes (e.g. that for safety or tolerability reasons such as a serious adverse event at least possibly related to the study drug) it is in the best interest of the subject to discontinue the study.

The subject becomes pregnant

A subject will be discontinued from the study when the QTc interval (QTcF; QTcB if ECG machine only shows QTcB) is higher than 500 msec. ECG events should be confirmed by repeat twice as soon as possible after the initial ECG, and the average value of the QTcB interval will be used to determine whether a subject should be discontinued. The subject will continue to be monitored by repeated 12-lead ECGs (at least every 60 min) until the ECG normalizes.

Because of limited information on the effects of JNJ-42165279 on the human liver function a subject will be discontinued from the study if either of the following occur:

- Aspartate transaminase (AST) and/or alanine transaminase (ALT) >3 x ULN (confirmed by repeat),
- Total bilirubin >2 x ULN (confirmed by repeat).

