3.3.2. Protocol Stopping Criteria

Medical monitoring by the sponsor will occur on a continual basis including laboratory and ECG data. A Data Review Committee (DRC) may be established to monitor data on an ongoing basis to ensure the continuing safety of the subjects enrolled in this study (see Section 11.8 Data Review Committee) if the frequency of discontinuations exceeds 10% of subjects or increases in liver transaminases of 5-fold over the ULN are observed. The committee will meet periodically to review interim data. After the review, the DRC will make recommendations regarding the safety and continuation of the study. The details will be provided in a separate DRC charter.

4. SUBJECT POPULATION^b

Approximately 143 subjects with MDD with anxious distress will be enrolled in the proof-of-concept study. Because it is of the interest to assess in this study the effect of FAAH inhibition on symptoms of anxiety and depression, additional assessments with anxiety and depression scales will be included.

^a This section has been amended per amendment INT-5

^b This section has been amended per Amendment INT-2.

The inclusion and exclusion criteria for enrolling subjects in this study and the prohibitions and restrictions are described in the following 3 subsections. If there is a question about the inclusion or exclusion criteria below, the investigator should consult with the appropriate sponsor representative before enrolling a subject in the study.

For a discussion of the statistical considerations of subject selection, refer to Section 11.1, Sample Size Determination.

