6. Has a current or recent history of clinically significant suicidal ideation within the past 6 months, corresponding to a score of 4 (active suicidal ideation with some intent to act, without specific plan) or 5 (active suicidal ideation with specific plan and intent) for ideation on the Columbia Suicide Severity Rating Scale (C-SSRS), or a history of suicidal behavior within the past year, as validated by the C-SSRS at screening or Day 1. Subjects with a prior suicide attempt, or prior serious suicidal ideation/plan ≥ 6 months ago, should be carefully screened for current suicidal ideation and only included at the discretion of the investigator.
7. Subject has a history of or current thyroid disease, thyroid dysfunction and is currently untreated for it. Subjects treated for thyroid disease may be enrolled following review of their records of diagnosis and treatment history by the investigator and with written concurrence with the sponsor's medical monitor to ensure disease/treatment stability and compliance.
8. Criterion modified by Amendment 2.
 - 8.1. Subject has clinically significant abnormal findings on physical examination, neurological examination or clinically significant abnormal vital signs indicative of untreated illness (such as infection or hypertension).
9. Criterion modified by Amendment 5.
 - 9.1. Subject has a clinically significant abnormal finding on 12-lead ECG such as QTcF (QTcB if ECG machine only shows QTcB) >450 msec for males and females, Left Bundle Branch Block, AV Block second degree or higher, permanent pacemaker or implantable cardioverter defibrillator (ICD) at screening or baseline (Day 1 predose), or any finding which in the opinion of the investigator is not appropriate and reasonable for the population under study. ECG recordings and vital signs may be repeated once and for questions on findings on the ECG a local cardiologist should be consulted.
10. Criterion modified by Amendment 5.
 - 10.1 Subject has a history of or current liver or renal insufficiency; clinically significant cardiac, vascular, pulmonary, gastrointestinal, endocrine, hematologic, rheumatologic, psychiatric, or metabolic disturbances (e.g. unstable situation needing monitoring or regular dose adaptations). Subjects with renal or liver function analytes significantly higher (more than 1.5 times the upper limit of normal) at screening are not eligible for the study.

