9.2.4. Electrocardiogram

Twelve-lead ECGs² will be collected at the time points listed in the Time and Events Schedule.

Only at Day 1 triplicate ECGs are required, i.e., 3 individual ECG tracings should be obtained as closely as possible in succession, but no more than 2 minutes apart. The full set of triplicates should be completed in less than 4 minutes.

During the study, the clinical investigator will review the ECG for immediate management and to mark abnormalities. A description of the overall assessment (i.e., normal or abnormal plus reason) will be made and a copy of the trace will be placed with the source data.

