17. ADMINISTRATIVE REQUIREMENTS

17.1. Protocol Amendments

Neither the investigator nor the sponsor will modify this protocol without a formal amendment by the sponsor. All protocol amendments must be issued by the sponsor, and signed and dated by the investigator. Protocol amendments must not be implemented without prior IEC/IRB approval, or when the relevant competent authority has raised any grounds for non-acceptance, except when necessary to eliminate immediate hazards to the subjects, in which case the amendment must be promptly submitted to the IEC/IRB and relevant competent authority. Documentation of amendment approval by the investigator and IEC/IRB must be provided to the sponsor. When the change(s) involves only logistic or administrative aspects of the study, the IRB (and IEC where required) only needs to be notified.

During the course of the study, in situations where a departure from the protocol is unavoidable, the investigator or other physician in attendance will contact the appropriate

sponsor representative (see Contact Information page(s) provided separately). Except in emergency situations, this contact should be made before implementing any departure from the protocol. In all cases, contact with the sponsor must be made as soon as possible to discuss the situation and agree on an appropriate course of action. The data recorded in the CRF and source documents will reflect any departure from the protocol, and the source documents will describe this departure and the circumstances requiring it.

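### Protocol 3.3.1 sets the 500 msec stopping limit on QTcF but decides discontinuation on average QTcB, so the two sentences can disagree for the same subject

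*Protocol*

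**What the plan says.** Protocol section 3.3.1 (Individual Stopping Criteria), in its current form as amended by INT-5, contains two consecutive statements on QTc.

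- The limit: a subject is discontinued "when the QTc interval (QTcF; QTcB if ECG machine only shows QTcB) is higher than 500 msec".
- The confirmation: the event is to be confirmed by two repeat ECGs, after which "the average value of the QTcB interval will be used to determine whether a subject should be discontinued". No limit is restated, so 500 msec has to be carried over from the limit sentence.

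Exclusion criterion 9.1 in section 4.2 follows the same order of preference as the limit sentence: "such as QTcF (QTcB if ECG machine only shows QTcB) >450 msec for males and females".

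The amendment log gives one aim of INT-5 as making the QTc instructions for stopping and exclusion more specific. The change it logs for section 3.3.1 concerns the limit sentence only. Protocol section 11.3 and SAP section 5.5 treat QTcB (Bazett) and QTcF (Fridericia) as separate variables, so the terms are not interchangeable in this trial. Nothing else in the protocol or SAP reconciles the two sentences.

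**The concern.** The limit sentence uses QTcF and allows QTcB only as a fallback. The confirmation sentence, which makes the actual decision, uses QTcB unconditionally. Where a machine shows only QTcB the sentences agree. Where it shows QTcF they name different quantities, and a site can point to either one.

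At stake is a mandatory individual stopping rule. If the confirmation sentence is followed literally, a subject with a slow heart rate whose average QTcF is confirmed above 500 msec may stay on study. A subject with a faster heart rate may be withdrawn although average QTcF is below 500 msec. Sites could apply the rule differently without either clearly deviating from the protocol.

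**Working it through.** The documents give no figure to reproduce here. The check is whether the two sentences can give different answers at plausible heart rates.

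**Inputs.** The 500 msec limit, its preference for QTcF and the use of average QTcB for the decision come from Protocol 3.3.1. The two corrections are named in Protocol 11.3 and SAP 5.5; their standard definitions are used. The heart rates and QT values are illustrative assumptions, not trial data. SAP Table 6 classes 45 to 90 bpm as normal.

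**Formulas.** With RR = 60/HR in seconds:

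- QTcB = QT / RR^(1/2)
- QTcF = QT / RR^(1/3)
- Hence QTcB/QTcF = RR^(−1/6) = (HR/60)^(1/6)

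If heart rate is the same in the averaged tracings, this ratio also holds for the averages, even when QT varies between them. The QTcF at which QTcB equals 500 is 500 / (HR/60)^(1/6).

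| HR (bpm) | QTcB/QTcF | QTcF when QTcB = 500 (msec) |
|---|---|---|
| 45 | 0.953 | 524.6 |
| 50 | 0.970 | 515.4 |
| 55 | 0.986 | 507.3 |
| 60 | 1.000 | 500.0 |
| 70 | 1.026 | 487.3 |
| 80 | 1.049 | 476.6 |
| 90 | 1.070 | 467.3 |

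**Below 60 bpm: kept with QTcF above 500.** The QT band runs from 500 × RR^(1/3), above which QTcF exceeds 500, to 500 × RR^(1/2), up to which QTcB does not:

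- 55 bpm: QT 514.7 to 522.2 msec
- 50 bpm: QT 531.3 to 547.7 msec
- 45 bpm: QT 550.3 to 577.4 msec

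Example at 50 bpm (RR = 1.2), with QT 540, 535 and 534 msec:

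- QTcF = 508.2, 503.5, 502.5; mean 504.7 (two repeats only: 503.0)
- QTcB = 493.0, 488.4, 487.5; mean 489.6 (two repeats only: 487.9)

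The limit sentence says discontinue; the confirmation sentence says keep.

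**Above 60 bpm: stopped with QTcF below 500.** Example at 80 bpm, with QTcF 505, 490 and 490 msec, the first tracing triggering the repeats:

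- Mean QTcF = (505 + 490 + 490)/3 = 495.0 (two repeats only: 490.0)
- QTcB = 1.049 × QTcF = 529.8, 514.1, 514.1; mean 519.3 (two repeats only: 514.1)

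Here average QTcF does not confirm the event, while average QTcB requires discontinuation.

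The protocol does not say whether the average covers all three tracings or only the two repeats. Both examples hold either way.

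**The case against.** The strongest reply is that this is an editing leftover with an obvious meaning. INT-5 set out to make QTcF the primary measure, criterion 9.1 shows the intended form, and a sensible investigator would read the confirmation sentence in that light.

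The harmful direction is also narrow. It needs a QTcF-displaying machine, a heart rate below 60 bpm and a QT inside the bands above. Entry excludes QTcF above 450 msec, so a rise of more than 50 msec is generally required. Protocol section 1.1 reports no clinically significant ECG changes in the Phase 1 ascending-dose studies, no adverse effect in the hERG and Purkinje fiber assays, and no relevant electrocardiographic changes in the dog study. In the other direction the rule errs on the cautious side.

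There are other safeguards too:

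- Section 3.3.1: "The subject will continue to be monitored by repeated 12-lead ECGs (at least every 60 min) until the ECG normalizes", and the investigator or sponsor may stop any subject on safety grounds.
- Section 3.3.2: "Medical monitoring by the sponsor will occur on a continual basis including laboratory and ECG data".
- Section 9.2.4: "the clinical investigator will review the ECG for immediate management and to mark abnormalities".
- Section 10.2 repeats the investigator's discretion to stop treatment, section 9.1.1 allows extra measurements after abnormal safety findings, and section 17.6 describes direct transfer of ECG data to the sponsor.

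All of this stands as a limit on how often the conflict would matter and how far it could go unnoticed. None of it says which QTc decides. The confirmation sentence is explicit and unconditional, so following it literally is not a misreading, and discretion to stop does not replace a defined mandatory criterion.

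**Conclusion.** The inconsistency is real and in operative text. At sites whose machines show QTcF, section 3.3.1 followed as written can keep a subject with confirmed average QTcF up to about 507 msec at 55 bpm, 515 at 50 bpm or 525 at 45 bpm. Once repeats are triggered, it can also stop a subject with average QTcF only just above 487 msec at 70 bpm, 477 at 80 bpm or 467 at 90 bpm. The slow-heart-rate direction is the one that matters for safety.

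These figures assume the standard Bazett and Fridericia formulas and the same heart rate in the averaged tracings. The documents give neither the number of sites whose machines show QTcF nor an expected frequency of QTc above 500 msec, so the number of subjects affected cannot be estimated; it is probably small. The primary efficacy analysis, sample size and type I error are not affected. The point should be fixed because it concerns a mandatory cardiac stopping rule and the correction is simple.

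**What to change.** In the confirmation sentence of Protocol 3.3.1, make the deciding value the average QTcF, with the average QTcB used only where the ECG machine shows QTcB alone. The limit and the decision then rest on the same quantity and match criterion 9.1. In the 50 bpm example the subject is discontinued (average QTcF 505); in the 80 bpm example the subject continues (average QTcF 495).

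The cost is one phrase, a protocol amendment and site notification. Section 17.1 applies: "Protocol amendments must not be implemented without prior IEC/IRB approval". INT-5, which carried the last QTc wording change along with other changes, was classed as substantial; INT-3, a correction of wording and inconsistencies, was not. The sponsor would need to decide which class fits an edit to a stopping rule. No new measurements are needed.

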3.3.2. Protocol Stopping Criteria

Medical monitoring by the sponsor will occur on a continual basis including laboratory and ECG data. A Data Review Committee (DRC) may be established to monitor data on an ongoing basis to ensure the continuing safety of the subjects enrolled in this study (see Section 11.8 Data Review Committee) if the frequency of discontinuations exceeds 10% of subjects or increases in liver transaminases of 5-fold over the ULN are observed. The committee will meet periodically to review interim data. After the review, the DRC will make recommendations regarding the safety and continuation of the study. The details will be provided in a separate DRC charter.

4. SUBJECT POPULATION^b

Approximately 143 subjects with MDD with anxious distress will be enrolled in the proof-of-concept study. Because it is of the interest to assess in this study the effect of FAAH inhibition on symptoms of anxiety and depression, additional assessments with anxiety and depression scales will be included.

^a This section has been amended per amendment INT-5

^b This section has been amended per Amendment INT-2.

The inclusion and exclusion criteria for enrolling subjects in this study and the prohibitions and restrictions are described in the following 3 subsections. If there is a question about the inclusion or exclusion criteria below, the investigator should consult with the appropriate sponsor representative before enrolling a subject in the study.

For a discussion of the statistical considerations of subject selection, refer to Section 11.1, Sample Size Determination.

4.1. Inclusion Criteria^a

Each potential subject must satisfy all of the following criteria to be enrolled in the study unless otherwise specified:

1. Subject must be a man or woman between 18 and 64 years of age, inclusive.
2. Subjects must have a primary DSM-5 diagnosis of MDD with Anxious Distress. Subjects with a diagnosis of comorbid Generalized Anxiety Disorder (GAD), Social Anxiety Disorder, or Panic Disorder may be included, if the investigator considers MDD with Anxious Distress to be the primary diagnosis (confirmed by an independent central rater through review of the MINI interview obtained by the site at screening).

Subjects must have been treated with an SSRI/SNRI antidepressant approved in this protocol at an adequate dose, as defined by the ATRQ, and for at least 6 continuous weeks, validated by an independent central rater contracted by the sponsor.

3. A HDRS₁₇ total score ≥ 18 at screening, assessed by a site rater and validated through review by an independent central rater contracted by the sponsor; and on Day 1 by site rater.
4. A HDRS₁₇ anxiety/somatization factor score ≥ 7 at screening, assessed by a site rater and validated through review by an independent central rater contracted by the sponsor; and on Day 1 by site rater.
5. Subjects must have a body mass index (BMI=weight/height²) between 18 and 35 kg/m², inclusive, at screening.
6. Criterion modified by Amendment 4.

6.1. Before randomization, a **woman** must be either:

- Not of childbearing potential: postmenopausal (>45 years of age with amenorrhea for at least 12 months, or any age with amenorrhea for at least 6 months and a serum follicle stimulating hormone (FSH) level >40 IU/L); permanently sterilized (e.g., tubal occlusion, hysterectomy, bilateral salpingectomy); or otherwise be incapable of pregnancy
- Of childbearing potential and practicing a highly effective method of birth control consistent with local regulations regarding the use of birth control methods for subjects participating in clinical studies (i.e. one that results in a less than 1% per year failure rate when used consistently and correctly). This may include:
 - Established and ongoing use of oral hormonal methods of contraception in

^a This section has been amended per Amendment INT-1, 3 and 4.

- combination with barrier methods.
- Established and ongoing use of patch, injected or implanted hormonal methods of contraception.
- Placement of an IUD or IUS.

Accepted barrier methods as indicated above include:

- condom with spermicidal foam/gel/film/cream/suppository
- occlusive cap (diaphragm or cervical/vault caps) with spermicidal foam/gel/film/cream/suppository

Note that a barrier method on its own is not sufficient.

- Male partner sterilization (the vasectomized partner should be the sole partner for that subject).
- True abstinence (when this is in line with the preferred and usual lifestyle of the subject).

Women must agree to continue using these methods of contraception throughout the study and for at least 3 months after receiving the last dose of study medication.

Note: If a woman of childbearing potential who is not heterosexually active becomes active after the start of the study, she must begin a highly effective method of birth control, as described above.

- **All women** must have a negative pregnancy test at screening and a negative urine pregnancy test on study day 1.
- **All women** must agree not to donate eggs (ova, oocytes) for the purposes of assisted reproduction during the study and for at least 3 months after receiving the last dose of study drug.

7. Criterion modified by Amendment 4.

7.1. **Men** who are sexually active with a woman of childbearing potential and have not had a vasectomy must agree to use a barrier method of birth control e.g., either condom or partner with occlusive cap (diaphragm or cervical/vault caps) with spermicidal foam/gel/film/cream/suppository for the duration of the study plus 3 months after receiving the last dose of study drug, and all men must not donate sperm during the study and for 3 months after receiving the last dose of study drug. In addition, their female partners should also use an additional method of birth control (which may include a hormonal method, an intrauterine device [IUD] or an intrauterine system [IUS]) for at least the same duration.

8. Subjects must be otherwise healthy for their age group or medically stable with or without medication on the basis of physical examination, medical history, vital signs, and 12-lead ECG performed at screening or at baseline. If there are abnormalities, they must be consistent with the underlying illness in the study population with written concurrence with the sponsor's medical monitor.
9. Subjects must be otherwise healthy or medically stable on the basis of clinical laboratory tests performed at screening. If the results of the serum chemistry panel [including liver enzymes, other specific tests], hematology, or urinalysis are outside the normal reference ranges, the subject may be included only if the investigator

judges the abnormalities or deviations from normal to be not clinically significant. This determination must be recorded in the subject's source documents and initialed by the investigator.

10. Subject must be willing and able to adhere to the prohibitions and restrictions specified in this protocol.
11. Subject must be willing and able to fill out self-administered questionnaires.
12. Subject must be able to be compliant with self-administration of medication.
13. Subject must be able to swallow the study medication whole with aid of water.
14. Subject must sign an informed consent document indicating that they understand the purpose of and procedures required for the study and are willing to participate in the study.

4.2. Exclusion Criteria^a

Any potential subject who meets any of the following criteria will be excluded from participating in the study unless otherwise specified:

1. Has any other current major psychiatric condition, including, but not limited to, MDD with psychotic features (lifetime), bipolar disorder (including lifetime diagnosis), obsessive-compulsive disorder, post-traumatic stress disorder, borderline personality disorder, eating disorder (e.g., bulimia, anorexia nervosa), or schizophrenia.

The MINI will be conducted by the primary investigator/sub-investigator (either a psychiatrist or Ph.D. psychologist) at Screening to confirm MDD as the primary diagnosis. In addition, an independent rater will confirm that the current depressive episode is valid as well as verifying any comorbid psychiatric conditions validated in the MINI. As noted, subjects with a diagnosis of comorbid GAD, Social Anxiety Disorder, or Panic Disorder may be included.

2. Has a length of current major depressive episode (MDE) >6 months.
3. Has initiated psychotherapy specific for MDD (such as cognitive behavioral, behavioral, or interpersonal therapy) for the current episode of depression within 6 weeks prior to screening. Subjects receiving psychotherapy can continue receiving psychotherapy provided this therapy has been stable in frequency for the last 6 months and will remain unchanged throughout the study treatment.
4. Has more than 1 failed treatment with antidepressants of adequate dose and duration in the current major depressive episode, prior to and not including the inadequate response to the current SSRI/SNRI antidepressant.

^a This section has been amended per Amendments INT-1, 2 and 5.

5. Has a history of resistance to medication treatment of major depressive episodes (≥ 3 lifetime treatment failures with approved antidepressants at adequate doses and duration).
6. Has a current or recent history of clinically significant suicidal ideation within the past 6 months, corresponding to a score of 4 (active suicidal ideation with some intent to act, without specific plan) or 5 (active suicidal ideation with specific plan and intent) for ideation on the Columbia Suicide Severity Rating Scale (C-SSRS), or a history of suicidal behavior within the past year, as validated by the C-SSRS at screening or Day 1. Subjects with a prior suicide attempt, or prior serious suicidal ideation/plan ≥ 6 months ago, should be carefully screened for current suicidal ideation and only included at the discretion of the investigator.
7. Subject has a history of or current thyroid disease, thyroid dysfunction and is currently untreated for it. Subjects treated for thyroid disease may be enrolled following review of their records of diagnosis and treatment history by the investigator and with written concurrence with the sponsor's medical monitor to ensure disease/treatment stability and compliance.
8. Criterion modified by Amendment 2.
 - 8.1. Subject has clinically significant abnormal findings on physical examination, neurological examination or clinically significant abnormal vital signs indicative of untreated illness (such as infection or hypertension).
9. Criterion modified by Amendment 5.
 - 9.1. Subject has a clinically significant abnormal finding on 12-lead ECG such as QTcF (QTcB if ECG machine only shows QTcB) >450 msec for males and females, Left Bundle Branch Block, AV Block second degree or higher, permanent pacemaker or implantable cardioverter defibrillator (ICD) at screening or baseline (Day 1 predose), or any finding which in the opinion of the investigator is not appropriate and reasonable for the population under study. ECG recordings and vital signs may be repeated once and for questions on findings on the ECG a local cardiologist should be consulted.
10. Criterion modified by Amendment 5.
 - 10.1 Subject has a history of or current liver or renal insufficiency; clinically significant cardiac, vascular, pulmonary, gastrointestinal, endocrine, hematologic, rheumatologic, psychiatric, or metabolic disturbances (e.g. unstable situation needing monitoring or regular dose adaptations). Subjects with renal or liver function analytes significantly higher (more than 1.5 times the upper limit of normal) at screening are not eligible for the study.
11. Subject has a history of malignancy within 5 years before screening (exceptions are squamous and basal cell carcinomas of the skin and carcinoma in situ of the cervix, or malignancy that in the opinion of the investigator, with written concurrence with the sponsor's medical monitor, is considered cured with minimal risk of recurrence).

12. If a subject is using a drug with moderate/strong CYP3A4 inhibiting or inducing properties at, or prior to, screening it must be discontinued within the equivalent of at least 5 half-lives prior to Day 1. Note: an existing medication should not be stopped solely for the purpose of the subject entering the study. Use of moderate and strong inhibitors and inducers of CYP3A4 are prohibited during the study (See [Attachment 12](#)).
13. Subject has a history of positive tests for hepatitis B surface antigen (HBsAg) or hepatitis C antibody (anti-HCV) positive, or other clinically active liver disease, or tests positive for HBsAg or anti-HCV at Screening.
14. Subject has a history of human immunodeficiency virus (HIV) antibody positive, or tests positive for HIV at Screening.
15. Subject has a history of drug or alcohol use disorder according to Diagnostic and Statistical Manual of Mental Disorders (5th edition) (DSM-5) criteria within 6 months before screening, or positive test result(s) for drugs of abuse (including barbiturates, opiates, cocaine, cannabinoids, amphetamines and benzodiazepines) at screening. A positive screen for benzodiazepines is allowed if related to recent treatment.
16. Subject has taken any disallowed therapies as noted in Section 8, Concomitant Therapy before the planned first dose of study drug.
17. Subject has known allergies, hypersensitivity, or intolerance to JNJ-42165279 or its excipients (refer to Investigator's Brochure).
18. Subject has received an investigational drug or used an investigational medical device within 3 months before the planned start of study or is currently enrolled in an investigational study.
19. Criterion modified by Amendment 5.
 - 19.1 Subject is a woman who is pregnant, or breast-feeding, or planning to become pregnant or is a man who plans to father a child, while enrolled in this study or within 3 months after the last dose of study.
20. Subject has any condition for which, in the opinion of the investigator, participation would not be in the best interest of the subject (e.g., compromise the well-being) or that could prevent, limit, or confound the protocol-specified assessments.
21. Subject has had major surgery, (e.g. requiring general anesthesia) within 8 weeks before screening, or will not have fully recovered from surgery, or has surgery planned during the time the subject is expected to participate in the study or within 4 weeks after the last dose of study drug administration.

Note: subjects with planned surgical procedures to be conducted under local anesthesia may participate.

22. Subject has a history of spontaneous, prolonged or severe bleeding.
23. Subject has donated one or more units (approximately 450 mL) of blood or had acute loss of an equivalent amount of blood within 90 days prior to study drug administration.
24. Subject is an employee of the investigator or study site, with direct involvement in the proposed study or other studies under the direction of that investigator or study site, as well as family members of the employees or the investigator
25. Subject is unable to comply with the study-specific requirements.

